### Details of Additional Program

#### Components:

#### ***iCardia & Remote BP***

**Monitoring:** iCardia is a secure password-protected remote monitoring system hosted in a HIPAA-compliant server at UI Health. iCardia provides a user-

friendly environment for authorized personnel to view participants' BP readings in real-time in the form of graphs and send personalized text-messages to participants' cell phones (as needed) through the Twilio communication platform (**Figure 3**). RAs will receive training on iCardia and schedule messages for study participants regarding appointments, medications, and goals. Text messages can be sent immediately, recurrently (e.g. daily), or at a scheduled date/time to one or more participants. All communications utilize Transport Layer Security with encryption.

***Addressing “White Coat HTN”:*** It has been suggested that a “white coat effect” (increase in BP

primarily in the medical care environment) can be present in as many as 20-33% of patients diagnosed with HTN. The use of wireless BP monitors with remote monitoring will address this issue and ensure that this is not a significant confounder in our study population. Following enrollment, subjects will be asked to check their BPs daily.

**Study Coordinator:** The study coordinator will be responsible for overseeing the 48-72 hour HTN outpatient referrals for all study participants and track compliance with follow-up appointments using a combination of EMR review and participant self-report. The study coordinator will also assist with transportation concerns, fax PACTH-c letters to non-UI Health providers, and be trained to use the Open Access scheduling system for selected FQHCs to facilitate appointment scheduling.

**Illinois Video Interpreter Network (IVIN) (all arms):** Translators versed in healthcare terminology are available by video 24 hours a day. In the rare circumstance that a Spanish-speaking study staff member is not available, the IVIN system will be employed to facilitate communication with the participant both at enrollment in the ED and during the PACTH-consultation.

**Patient In-Person Clinic Follow Ups (all arms):** Following enrollment and randomization, **there will be up to three additional in-person visits at 3 and 6-months for BP measurements.** Staff will be blinded to study arm assignment. These repeat visits will occur in the PACTH-c space (adjacent to the ED in Suite 1100 of the hospital) and be conducted by trained RAs using study protocols and the AHA guidelines.

**Participant Retention (all arms):** Attrition is a challenge for follow-up data collection, particularly in underserved populations. We plan to use several strategies including: **1)** monetary reimbursement for in-person data collection (\$50 for their 3 month follow up and \$50 for their 6 month follow-up post-randomization); \$50 will also be given to participants in the event they are asked to return in 1 year); \$100 for participants that miss their 3 month follow-up but come in for their 6 month follow-up (\$50 for missed 3 month and \$50 for 6 month which is main outcome); **2)** periodic phone calls to verify address and phone data (at 1, 3, 5, 6, 9, and 11 -months post-enrollment); **3)** use of secondary alternative contact information; **4)** text messaging 24 hours prior to follow-up appointments; **5)** mailing birthday/holiday cards; and **6)** monthly newsletters containing recruitment updates. Co-Investigator [name] has demonstrated success in participant

retention in numerous studies involving high-risk populations with attrition rates between 8-10%. In our R56 trial (IRB protocol # 2015-0323), we had a final attrition rate of 25% (9-month follow-up) due to transportation difficulties and loss of phone contact. To limit the attrition rate for this proposal, we will provide ride share, public transit, and parking vouchers as needed, and will provide smartphones to Arm 2 study participants without phones. Geocoding of our patient population demonstrated that the majority of individuals live within a 5-10-mile radius of UI Health. We are confident that these retention strategies will limit our attrition rate to no more than 20%.

**Assessment of Impact of Intervention on the Racial Disparity Associated with Uncontrolled**

**HTN and Mediating Factors (Aim 3):** We will examine whether the intervention reduces racial disparities associated with uncontrolled HTN, i.e. is this intervention as effective in ethnic minorities as non-minorities. This will be an exploratory analysis and will primarily focus on changes in cardiovascular risk score. In addition, we will measure two potential mediating factors multiple times during the trial: **1)** adherence to follow-up visits, and **2)** the Modified Morisky Scale. All participants will receive phone calls at predetermined times to determine **primary care engagement**. All communication will be scripted and include: **1)** whether follow-up visits with the PCP have occurred or are scheduled; and **2)** the Modified Morisky Scale to assess current HTN medication use and understanding. The appropriate surveys will be administered by RAs at the time of enrollment, by phone at 1 and 5 months, and at 3 and 6 months during the in-person visit. Shorter calls will be made at 2, 5, and months to schedule the 3 and 6-month appointments.

**Research Material:**

All research materials obtained during the course of this study will be for research purposes. The materials that will be obtained from the human subjects that participate in this study are blood pressure measurements, as well as assessments on medication adherence, HTN knowledge, and patient activation.

**New Data:**

Demographic data and blood pressure data, both provider-obtained and/or from patient-recorded home measures, will be obtained for all participants. New data will also include level of medication adherence, hypertension knowledge, and ASCVD risk score.

### **Linkages to Subjects:**

All information collected in this study is confidential and all data will be transformed into anonymously-coded identifiers for each subject prior to analysis. We use a double coding system to maintain the confidentiality of information. Only [name] (PI) and study personnel will be able to link information to subjects. This is necessary because patients will be followed for a total of six months after discharge so participants will need to be tracked during this time. All data will be stored electronically on REDCap.

### **For Specimen Collection Studies**

We will collect a single fingerstick of blood to measure HDL cholesterol levels for the ASCVD risk score.

### **For Studies that Collect Existing or Prospective Data**

Prospective data to be collected from all subjects include blood pressure measurements. Subjects in the E intervention will have a series of risk assessment tools designed to be efficient, patient-centered and educational for participants in an emergency department setting. Through the intervention, participants will learn more about hypertension management and complications associated with uncontrolled BP.

Study data will be maintained for 7 years post study completion and then will be destroyed.

## **7.0 EXPECTED RISKS/BENEFITS**

### **Potential Risks:**

The potential risks associated with this study are: (1) The potential for loss of privacy or confidentiality of health information. (2) Possible discomfort with assessments, however all measures are noninvasive with the exception of a single fingerstick of blood for the ASCVD risk score, so little discomfort is expected. (3) For the group that receives the Smartphone-enabled

Blood Pressure Monitoring Kit (group 2), participants may potentially feel annoyed or irritated with the frequency of notifications and/or text-message reminders they receive. For the app notifications, participants will have the option of turning off the notifications or change their frequency. The Research Assistants will show participants how to do this when they set up the app on the participant's phone. For the text-messages, participants will have two options; the first option is to contact the research staff and ask them to reduce the number of text-messages they receive. The second option is to reply to one of the text-messages with the word "STOP". Our system will automatically stop sending text-messages after that. However, if participants want to re-subscribe, they can reply with the word "START" and the text-messaging program will resume.

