The Usual Care group (Arm 1) will receive preprinted discharge instructions and an outpatient referral. This group represents standard of care. All other interventions in arm 2 are research activities.

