**Table 1: Intervention Components by Arm \***

Arm 1: Usual Care (N=385)				
Arm 2: E Intervention (N=385)				
Intervention Components by Arm	Baseline	Quarterly	Mid-point	End
Location	ED	Phone	UI-Health Suite 1600	UI-Health Suite 1600
Time Point in Months (0=ED discharge)	0	1, 3, 5	3	6
Duration	10-20 min	5 min	10-20 min	20 min
BP Measured	1, 2		1, 2	1, 2
Clinical Data (from med chart)	1, 2			

Atherosclerotic Cardiovascular Disease (ASCVD) Risk Score	1,2			1,2
Hypertension Knowledge Assessment	1, 2			1, 2
Modified Morisky Scale	1, 2	1, 2	1, 2	1, 2
Patient Activation Measurements Survey (PAM)	1, 2	1, 2	1, 2	1, 2
Verify patient contact info	1, 2	1, 2	1, 2	
Bedside Echocardiogram Education	2			
Hypertension Education Video	2			
PACT-Hypertension (Pharmacy) Consultation:	2			
Home BP Monitoring Training and Reminders	2	2	2	

\*We may ask participants to return for a follow up at one year post-enrollment at which time all assessments and surveys performed at recruitment will be repeated.

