**PACHT-c:** All participants randomized to the E intervention will have a focused consultation with either a clinical pharmacist or an APN. To ensure consistency throughout the trial, the PACHT-c intervention will be standardized and interchangeable between the clinical pharmacists and APNs. During the day, the on-site ED clinical pharmacist will provide consultations. During evening and weekend hours, consultations will be provided by the APN located in the ED Clinical Decision Unit (CDU). The CDU is open 24 hours a day, 7 days a week. During this consultation, the pharmacist/APN repeats the BP measurement; reviews the screening

assessments; and reviews general principles of BP control including nutrition, exercise, and smoking cessation. BP will be managed according to the current published guidelines available regarding initiation of first-line antihypertensive medications. Patients with BP  $\geq 140/90$  mmHg may be started on antihypertensive medications by the provider during the consultation if appropriate. All PACTH-c clinic notes will be accessible in the EMR, which is shared between both the ED and our FQHC, Mile Square Health Center. No tests will be ordered during the pharmacy follow-up.

[figure not shown]
Based on our pilot trial (IRB Protocol # 2015-0323) the E intervention takes about 20-30 minutes following randomization. Once patients are identified for discharge, the wait time before physically leaving the ED provides ample time to consent and complete the initial assessments based on participant randomization at the bedside without adding delays. Participants will be approached for study participation after they have been identified for discharge and BEFORE being physically discharged from the ED.

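### Arm 2 may start antihypertensives, yet section 7.0 names no drug risk, no written call or visit item asks about symptoms, and home BP readings have no low action limit

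*Combined protocol and SAP*

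**What the plan says.** **Drug start.** Section 6.0, Details of Intervention Components, PACHT-c: patients at or above 140/90 mmHg "may be started on antihypertensive medications by the provider during the consultation if appropriate". After describing usual care, section 6.0 adds "All other interventions in arm 2 are research activities".

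**Stated risks.** Section 7.0, Potential Risks, begins "The potential risks associated with this study are: (1) The potential for loss of privacy or confidentiality of health information". Its other two entries are discomfort with assessments (including the fingerstick) and irritation with notifications and texts. Section 10.0/11.0 calls the risk minimal.

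**Adverse events.** Table 2 (section 10.0/11.0) puts rash, angioedema, cough after a new drug, leg edema, lightheadedness or fainting, and orthostatic hypotension under the study-related heading. Laboratory changes attributed to a drug side effect come under the non-study heading. The accompanying text provides a DSMB, weekly team meetings, a documented safety monitoring plan and a judgement of cause for each event.

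**Contacts and data.** The schedule is headed "Table 1: Intervention Components by Arm": calls at months 1, 3 and 5, visits at months 3 and 6. For the Aim 3 calls, "All communication will be scripted and include" is followed by two items, primary care follow-up and the Modified Morisky Scale. Research Material lists "blood pressure measurements, as well as assessments on medication adherence, HTN knowledge, and patient activation". New Data adds demographics and says "New data will also include level of medication adherence, hypertension knowledge, and ASCVD risk score".

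**Home readings.** Section 6.0 twice describes these as a safety feature against lowering BP too far. Research assistants view them remotely. The one numerical limit is above 180/120, where the participant is to contact a physician.

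**The concern.** The trial can put a new drug into arm 2, and its own event table expects drug harms to count as study-related, but the risk section is written as if no drug were involved. A DSMB or IRB reader who relies on section 7.0 and the minimal-risk sentence gets a different picture from a reader of Table 2.

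Table 2 and the reporting text say how to describe and pass on an event once it is known. They do not say when anyone asks. The first scheduled study call is at month 1, and symptoms are not among its listed content.

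There is also a problem of comparison. Arm 2 alone receives behavioral texts, reminders and calls for missed readings. With no common question in both arms, the harm counts partly measure how often each arm talks to staff. An excess in arm 2 could reflect contact rather than treatment.

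**Working it through.** No figure in the plan bears on this point, so the check is a reading of the relevant sections side by side.

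**1. Risk list against event table.** Section 7.0 has three risks, none from a drug. Table 2 has seven study-related rows. At least five are recognizable drug harms (angioedema, cough after a new drug, leg edema, lightheadedness or fainting, orthostatic hypotension), and rash could be a sixth. The two sections disagree.

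**2. Event table against the relatedness rule.** The text before Table 2 says the team will try to establish cause and judge relatedness for each event. Yet a laboratory change that the table itself describes as a drug side effect sits under a heading that already calls it non-study related. A drop in potassium after a drug started at the consultation would therefore be filed against its own description.

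**3. Is there a symptom question?**
- Table 1 has 11 activity rows: BP, chart data, ASCVD, knowledge, Morisky, PAM, contact check, echo education, video, consultation, home BP training. None is a symptom enquiry.
- The call script names two items; neither is one. The Morisky scale measures adherence.
- Research Material and New Data together give six distinct items: BP, adherence, knowledge, activation, demographics, ASCVD score. None is symptoms.
- Other calls appear under Participant Retention (months 6, 9 and 11 in addition to 1, 3 and 5) and under Aim 3 (month 2). Their stated purposes are contact details and scheduling.

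These lists are not exhaustive: Table 1, for example, has no row for the primary care enquiry that the script contains. The supportable statement is that no such question is written, not that none will be asked.

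**4. Home readings.**

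| Trigger | Action written |
|---|---|
| Above 180/120 | Participant contacts a physician |
| Missed readings, 7 or 14 days (two places in section 6.0 differ) | Research assistant phones |
| Low reading | None |

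The general description accepts as few as two readings a month, and section 7.0 lets participants switch off notifications.

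**5. Could low BP occur?** Section 6.0 says a white-coat effect may be present in 20-33% of diagnosed patients. Section 2.0 cites continued elevation at outpatient follow-up in 59% of men and 78% of women, so 100 − 59 = 41% and 100 − 78 = 22% were not elevated. These are background figures, not rates for this trial. They show only that some patients treated on an ED reading may usually run lower.

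**6. Burden of asking.** Three calls plus two visits make 5 contacts. Across 770 participants that is at most 770 × 5 = 3,850 short questions before attrition, or 385 × 5 = 1,925 per arm.

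**The case against.** The strongest reply is that the plan already has a safety system. It has a DSMB of three external members, weekly meetings, and a safety monitoring plan that is not in the documents and may contain the missing steps. The PACHT-c text requires management by current guidelines. A coordinator oversees the 48-72 hour referral, tracks attendance, helps with transport and sends consultation letters to outside providers. Table 2 defines hypertensive urgency partly by clinic readings between study visits, which suggests that events are reviewed at visits. Prescribing is at the provider's discretion and could be seen as clinical care; that it falls within the arm 2 research activities is an inference.

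Much of this stands, and it rules out several stronger readings that a reader might infer:
- **That the plan ignores drug harm.** Table 2 recognizes it as study-related.
- **That nobody looks for low BP.** Home readings are requested, viewed by research assistants and intended for this purpose, and BP is measured at months 3 and 6. What is missing is a limit and a responder.
- **That events surface only if volunteered.** Review at visits is plausible, though unwritten.
- **That laboratory monitoring is barred.** "No tests will be ordered during the pharmacy follow-up" may cover that encounter alone and does not bind the referral clinic.
- **That participants are not told of drug risks.** The consent form was not available.

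The reply does not remove the disagreement between section 7.0 and Table 2, the preset relatedness of drug-related laboratory changes, the unwritten symptom question or the absent low-BP limit. Oversight bodies act on events that have reached them, and referral protects those who attend; attendance is itself something the trial measures.

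**Conclusion.** The point holds in a limited form and should be addressed. The protocol permits a drug start in arm 2 and expects drug harms as study-related events. Its risk section omits them, one drug-related category is assigned in advance to the non-study group, no written contact item asks about symptoms, and the home-reading safeguard has no low threshold, escalation route or clinician behind it.

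The size can be stated only as exposure: up to 385 participants have the consultation, the number started on a drug is not given and none is assumed, and no harm rate can be estimated. Between-arm ascertainment bias is likely in direction (more contact in arm 2) but cannot be quantified.

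The conclusion assumes that the unavailable safety monitoring plan does not already supply the symptom question and the low-BP rule. If it does, those two parts reduce to a cross-reference; the inconsistencies in section 7.0 and Table 2 remain. Nothing here affects the sample size or the primary SBP analysis.

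**What to change.** 1. **Symptom question.** Add one question on symptoms and side effects, based on Table 2 and worded identically in both arms, to the calls at months 1, 3 and 5 and the visits at months 3 and 6. At visits, ask it after BP is measured. Research assistants make both calls and visits, so earlier answers could reveal the arm before the month 6 outcome; keep answers from the staff who measure outcome BP.
2. **Low home-BP limit.** The investigators and DSMB choose an action value. Name the clinician role that responds and the route from research assistant to clinician.
3. **Text.** Add to section 7.0 the risks of a drug started at the consultation, make the minimal-risk sentence in section 10.0/11.0 agree, and judge relatedness of drug-related laboratory changes case by case.

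The cost is a protocol amendment, a few minutes at each of five existing contacts, and some clinician time for alerts. An extra early call for arm 2 is not asked for: it would add an arm-specific contact in a trial that studies engagement and adherence as mediators. Study-run laboratory follow-up is not asked for either, since the referral clinic may provide it and the need depends on prescribing that the plan does not specify.

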#### **Alternative Treatments/Procedures:**

Patients that decide not to enter this study will be informed that there is other care available, such as a referral to see a primary care doctor at the Mile Square Health Center. The study research assistant will discuss these options with the patient and let them know that they do not have to be in this study to be treated for hypertension.

#### **Potential Benefits of Proposed Research to Subjects and Others:**

Subjects may not directly benefit from participation in the research. Indirect benefits include expansion of risk assessment intervention to include emergency departments.

#### **Importance of the Knowledge to be Gained:**

Uncontrolled hypertension contributes significantly to cardiovascular morbidity and mortality and is more frequently encountered among patients presenting to the emergency department (ED), which serves as the point of entry into the health care system for many high-risk patient populations, particularly minorities. If our results are as expected, our clinically relevant study has the potential to provide new insights into increasing motivation, follow-up rates, and consequently, treatment compliance and blood pressure control in a predominately underserved hypertensive population.

## **8.0 DATA COLLECTION AND MANAGEMENT PROCEDURES**

### **Data Characteristics:**

All data forms will be initially developed and tested on paper; Spanish language versions of participant questionnaires will be prepared and back-translated to English prior to obtaining certified translations; after thorough pilot testing, paper forms are to be converted to equivalent electronic data entry forms with use of REDCap. REDCap (Research Electronic Data Capture) is a secure, web-based application designed to support data capture for research studies, providing: 1) an intuitive interface for validated data entry; 2) audit trails for tracking data manipulation and export procedures; 3) automated export procedures for seamless data downloads to common statistical packages; and 4) procedures for importing data from external sources. At UI Health, REDCap is hosted on secure servers located in and supported by the Institute for Health Research and Policy (IHRP). Project staff will be trained in the use of REDCap for entry of study data. Appropriate logic and limits checking (including cross-form validity checks) will be implemented in REDCap to facilitate accurate and consistent data entry. Where practical, study data will be directly entered into the REDCap database by clinical staff. Alternatively, information can be captured on paper and entered into the system from the forms. Routinely throughout the study the REDCap database will be downloaded into a secure virtual computing environment (virtual servers and virtual workstations secured behind software and hardware firewalls) available through the IHRP. Study information within the virtual environment will be available for participant tracking activities such as production of result and reminder letters, scheduling of interim telephone contacts, and scheduling and tracking of follow-up visits. Regular quality control and data cleaning/ error reports will be produced which identify missing, out of range, and questionable values. These reports will be reviewed with study staff every two weeks. Errors will remain on reports until they are resolved. Statistical analyses prior to the 3, 6, and 12- month outcome evaluations will be limited to quality control, enrollment and drop out reporting and participant demographics. No interim looks are anticipated but quality control and data entry errors and omissions will be continuously monitored and reported to staff for remediation.

